### **9.4.2. Secondary Analyses**

For Phase 1, ORR at Day 28, defined as the proportion of subjects demonstrating a CR, VGPR, or PR will be summarized by cohort. Their applicable 95% CI will be provided

For Phase 2,  $C_{\max}$ ,  $C_{\min}$ ,  $T_{\max}$ , AUC, and Cl/F assessed at Day 7 will be summarized.

For Phase 1 and 2, all the secondary analyses will be conducted for the efficacy evaluable population by cohort. Summary statistics and their applicable 95% CI will be provided.

- ORR, defined as the proportion of subjects demonstrating a CR, VGPR, or PR at Days 14, 56, and 100. Summary statistics and applicable 95% CI will be provided.
- NRM rate, defined as the proportion of subjects who died due to causes other than underlying hematological disorders at Months 6, 9, 12, and 24. Cumulative incidence rates will be provided. Summary statistics and applicable 95% CI will be provided.
- Duration of response for responders will be calculated. The DOR is defined from the time of the onset of response to either progression or death.
- Time to response, defined as the interval from treatment initiation to first response, will be summarized by cohort.
- Relapse rate of malignant and nonmalignant disorders, defined as the proportion of subjects whose underlying disease relapses. The cumulative incidence rate and summary statistics will be provided.

- Malignant and nonmalignant disorders relapse-related mortality rate, defined as the proportion of subjects whose underlying disease relapses and has a fatal outcome. The cumulative incidence rate and summary statistics will be provided.
- FFS rate at a timepoint, defined as the proportion of subjects who are still alive, have not relapsed, have not required additional therapy for aGVHD, and have not demonstrated signs or symptoms of cGVHD. The Kaplan-Meier method will be used. Summary statistics will be provided.
- Overall survival, defined as the interval from treatment initiation to death due to any cause. The Kaplan-Meier method will be used. Summary statistics will be provided.
- Clinical safety data (eg, AEs, infections) will be tabulated and listed.
- Incidence rate of secondary graft failure, defined as > 95% recipient cells any time after engraftment with no signs of relapse OR retransplantation because of secondary neutropenia ( $< 0.5 \times 10^9/L$ ) and/or thrombocytopenia ( $< 20 \times 10^9/L$ ) within 2 months of transplant.
- Average and cumulative corticosteroid dose at Days 28, 56, 100, and 180; proportion of subjects who discontinue corticosteroids at Days 56 and 100.
- Proportion of subjects who discontinue immunosuppressive medication at Days 56 and 100.
- Incidence rate of aGVHD flares through Day 100.
- Incidence rate of cGVHD at Days 180 and 365.

[REDACTED]

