**Table 1: Study Objectives and Endpoints**

Objectives	Endpoints
Phase 1 (Safety run-in for first 10 subjects in each cohort)	
Primary	
To assess the safety and tolerability of itacitinib in combination with corticosteroids in pediatric subjects with Grade II to IV SN-aGVHD.	

Frequency, duration, and severity of AEs and SAEs

Changes in vital signs and clinical evaluations.

Changes in clinical laboratory blood samples.

To evaluate the PK of itacitinib when administered in combination with corticosteroids.	

<math>C_{max}</math>, <math>C_{min}</math>, <math>T_{max}</math>, AUC, and Cl/F assessed at Day 1, 7, and 28.

Secondary	
To assess the efficacy of itacitinib in combination with corticosteroids in terms of ORR at Day 28 in pediatric subjects with aGVHD.	

ORR at Day 28, defined as the proportion of subjects demonstrating a CR, VGPR, or PR.

Phase 2 (Final analyses to combine all subjects within a cohort)	
Primary	
To assess the efficacy of itacitinib in combination with corticosteroids in terms of ORR at Day 28 in pediatric subjects with aGVHD.	

ORR at Day 28, defined as the proportion of subjects demonstrating a CR, VGPR, or PR.

Secondary	
To evaluate the PK of itacitinib when administered in combination with corticosteroids.	

<math>C_{max}</math>, <math>C_{min}</math>, <math>T_{max}</math>, AUC, and Cl/F assessed at Day 7.

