## **5. TREATMENT**

### **5.1. Study Drug and Treatment Assignment**

#### **5.1.1. Subject Numbering and Treatment Assignment**

Each subject will be identified in the study by a subject ID number, which is a combination of the site ID and subject number. Site staff should contact the IRT to obtain the subject ID number during screening.

Site staff will contact the IRT to obtain the initial study drug assignment. The investigator or designee will select the assigned bottles of study drug from their stock that correspond to the number provided by the IRT, record the bottle numbers in the eCRF, and dispense the study drug to the subject. All subsequent dispensing of study drug should follow this process. Full details will be provided in the IRT manual.

All subject numbers will be 6 digits; the first 3 digits will be the site number and the last 3 digits will be the subject's number. This subject number will be maintained throughout the study and will not be reassigned. Subjects who withdraw consent or discontinue from the study after being assigned a subject number will retain their initial number.

If a subject is mistakenly given a bottle of study drug that is not the bottle assigned by the IRT, then the IRT help desk must be notified immediately. The reason for the misallocation of the study drug must be documented by the study site.

For subjects who signed an ICF but are not allocated and for subjects who are allocated but were not treated, refer to the eCRF Completion Guidelines for instruction on which eCRFs to complete.

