When the severity of an AE changes over time for a reporting period (eg, between visits), each change in severity will be reported as a separate AE until the event resolves. For example, 2 separate AEs will be reported if a subject has Grade 1 diarrhea, meeting the definition of an AE, that lasts for 3 days before worsening to a Grade 3 severity. The Grade 1 event will be reported as an AE with a start date equal to the day the event met the Grade 1 AE definition and a stop date equal to the day that the event increased in severity from Grade 1 to Grade 3. The Grade 3 event will also be reported as an AE, with the start date equal to the day the event changed in intensity from Grade 1 to Grade 3 and a stop date equal to the day that the event either changed severity again or resolved. For analysis purposes, this will be considered 1 AE for this subject, and the highest reported severity will be used.

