## 9. STATISTICS

### 9.1. Study Populations

The populations to be analyzed include the following:

- Efficacy evaluable population: Subjects enrolled into the study.
- Safety evaluable population: Subjects enrolled into the study who received at least 1 dose of study drug.
- Pharmacokinetic evaluable population: Subjects who receive at least 1 dose of study drug and provide at least 1 plasma sample (1 PK measurement) after study drug administration will be considered as potential PK evaluable subjects. The study pharmacokineticist will review data listings of study drug administration and sample records to identify subjects to be excluded from analyses of PK data.

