## **9.5. Safety Analyses**

### **9.5.1. Adverse Events**

A TEAE is either any AE reported for the first time or worsening of a pre-existing event after first dose of study drug. Analysis of AEs will be limited to TEAEs, but data listings will include all AEs, regardless of their timing to study drug administration. Adverse events will be tabulated by the MedDRA preferred term and system organ class. Severity of AEs will be based on the NCI CTCAE v4.03 ([NCI 2010](#)).

- The subset of AEs considered by the investigator to have a relationship to study drug will be considered to be treatment-related AEs. If the investigator does not specify the relationship of the AE to study drug, the AE will be considered treatment-related. The incidence of AEs and treatment-related AEs will be tabulated.

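### Section 9.4.2 puts the secondary AE, infection and graft-failure summaries on all enrolled children rather than on those dosed; any bias can only lower AE rates, and it is small and conditional.

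*Combined protocol and SAP*

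**What the plan says.** Section 9.1 defines two populations that matter here: "Efficacy evaluable population: Subjects enrolled into the study", and "Safety evaluable population: Subjects enrolled into the study who received at least 1 dose of study drug". Only the second has a dosing condition.

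Section 9.4.2 then says "For Phase 1 and 2, all the secondary analyses will be conducted for the efficacy evaluable population by cohort". Its list mixes efficacy and safety items. Among the latter are "Clinical safety data (eg, AEs, infections) will be tabulated and listed" and the incidence of secondary graft failure. Table 1 makes both of these Phase 2 secondary endpoints. In Phase 1, AEs are a primary endpoint and fall under Section 9.4.1, which names no population.

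Section 9.5, the dedicated safety section, names no population either. In the text that can be read, the safety evaluable population is attached to no analysis. Section 9.5.1 adds that "Analysis of AEs will be limited to TEAEs", meaning events that first appear or worsen after the first dose. Section 5.1.1 gives data-entry instructions "for subjects who are allocated but were not treated", so children who never start treatment are foreseen.

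**The concern.** The only population the plan ties to AE tabulation is the efficacy one. A never-dosed child has no treatment-emergent events by definition, so including that child adds to the denominator and nothing to the numerator. The error therefore has a fixed direction: the drug can look safer than it is, never less safe.

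The denominator also matters for comparison with adults. Section 9.6 lets pediatric dosing in later cohorts depend partly on whether safety differs from that in adult GVHD patients, and the adult AE rates quoted in the protocol are on treated participants. The two sets of rates should share a denominator.

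**Working it through.** **1. The protocol's own figures.** Section 1.4.2 describes an adult study with 30 randomized, 1 of whom withdrew before treatment, leaving 29 treated. Taking each AE percentage as x/n:

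| Adult study event | x | Printed | x/29 | x/30 |
|---|---|---|---|---|
| Fatal TEAE | 9 | 31.0% | 31.0% | 30.0% |
| Serious TEAE | 22 | 75.9% | 75.9% | 73.3% |
| Discontinuation for a TEAE | 15 | 51.7% | 51.7% | 50.0% |

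All three printed values reproduce on 29. Section 1.4.4 agrees: thrombocytopenia at 14.3% and 26.7% fits 2/14 and 4/15, and 6/29 = 20.7% overall. (Sections 1.4.2 and 1.4.4 disagree on which dose cohort the untreated subject belonged to; the total of 29 does not depend on it.)

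**2. Dilution in this study.** Let E be the number enrolled, u the number never dosed and x the number with a given TEAE. The rate is x/(E - u) on the dosed population and x/E on the enrolled population. Their ratio is (E - u)/E. Section 9.2 gives E of up to 30 per cohort. The documents give no value for u, so 0 to 3 is an assumed range.

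| u of 30 | Factor | A true 50% reads as |
|---|---|---|
| 0 | 30/30 = 1.000 | 50.0% |
| 1 | 29/30 = 0.967 | 48.3% |
| 2 | 28/30 = 0.933 | 46.7% |
| 3 | 27/30 = 0.900 | 45.0% |

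The relative reduction is 3.3% to 10% for one to three undosed children.

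**3. Size against precision.** Exact (Clopper-Pearson) 95% intervals are 32.5-70.6% for 15/29 (51.7%) and 31.3-68.7% for 15/30 (50.0%). The shift of 1.7 points compares with a half-width of about 19 points.

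**4. Whether it would arise.** The only never-dosed rate in the documents is the adult 1/30. If it applied here, the chance of at least one undosed child in a cohort of 30 would be 1 - (29/30)^30 = 64%. That rate is poorly known. Its exact 95% interval is 0.084% to 17.2%, and putting those limits into the same formula gives 2.5% to 99.7%. The documents do not settle the frequency.

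**5. Secondary graft failure.** This item is not restricted to treatment-emergent events, so the one-way argument does not strictly apply. An undosed child could contribute an event as well as a denominator count. Either way, the child carries no information about the drug.

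**The case against.** The strongest reply is that enrolled may simply mean dosed. Section 7.4 equates enrollment with Day 1, and Section 6.1 mentions enrollment and administration of treatment together. Section 5.1.1 speaks of allocated, not enrolled, children who go untreated. On that reading the two populations nearly coincide and the effect vanishes. This stands as a limit on size, but it does not rescue the text: if enrollment implied a dose, the dosing clause in the safety definition of Section 9.1 would be redundant. Enrollment is nowhere defined relative to first dose.

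A second reply is that the analysis is descriptive (Section 9.3 rules out formal tests) and the shift is small beside the confidence interval. That is right, and it bears on priority.

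A third is that Section 9.5.3 refers to a Statistical Analysis Plan, which may name the safety population. No separate text of it is in the document supplied. If it did so, it would contradict Section 9.4.2, which would still need correcting.

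Two stronger readings are tempting and are not supported:

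- A reader might infer that one undosed child among the 10 in the Phase 1 run-in would distort its AE rates substantially. But Phase 1 AEs are a primary analysis outside the quoted sentence. Under Sections 4.1.1 and 4.3.2, the 10 evaluable subjects must have had at least 21 of 28 days of treatment or a DLT. The DLT stopping rule in Section 9.8 counts evaluable subjects and is unaffected.
- A reader might infer from Section 8.1.2 that the duration of severe AEs will be overstated. For an event that changes grade, it says "For analysis purposes, this will be considered 1 AE for this subject, and the highest reported severity will be used", and Table 1 lists "Frequency, duration, and severity of AEs and SAEs" as a Phase 1 primary endpoint. But nothing says duration will be tabulated by grade or taken from the merged record. Whole-episode duration is unbiased, and the dates at each grade are recorded separately. At most, the protocol does not say whether AE duration means the whole episode or time at each grade.

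**Conclusion.** The population sentence in Section 9.4.2 is wrong as written for AEs, infections and secondary graft failure. The consequence is small and conditional. It is nil if every enrolled child is dosed, and a relative 3-10% reduction in AE rates with one to three undosed per 30, always towards fewer AEs. This rests on reading enrolled literally, as Section 9.1 does, and on an assumed range for the number undosed. It does not show that AE rates will in fact be diluted. It shows that the plan permits it and leaves the right population unused.

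**What to change.** In Section 9.4.2, limit the population sentence to the efficacy endpoints. In Sections 9.4.2 and 9.5, state that AEs, infections and secondary graft failure are analysed on the safety evaluable population. It would help to define enrollment relative to first dose in Section 9.1. As an optional clarification, say in Section 9.4.1 whether AE duration means the whole episode or time at each grade; the dates required by Section 8.1.2 support either.

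The cost is a few sentences of text. No new data, visits or subjects are needed.

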### **Statistical Methods:**

Approximately 150 pediatric subjects will be enrolled into the study. Sample size is based on the clinical feasibility and consideration.

Phase 1:

Ten subjects will be enrolled into each cohort (Cohort 1: 12 to < 18 years old, Cohort 2: 6 to < 12 years old, Cohort 3: 2 to < 6 years old, Cohort 4: weighing > 8 kg to < 2 years old, and Cohort 5: 28 days old to weighing  $\leq$  8 kg). All AEs and all SAEs will be summarized. Dose-limiting toxicity will be defined as the occurrence of any of the toxicities below, occurring up to and including Day 28:

- Grade 4 neutropenia lasting more than 7 days or a  $\geq$  90% decrease in ANC from baseline
- Platelet count  $< 10 \times 10^9/L$  that can be reasonably attributed to study treatment, and does not recover after 2 weeks. Recovery is defined as platelets  $\geq 20 \times 10^9/L$  in the absence of platelet transfusion in the 7 days preceding the platelet recovery date. In case the platelet count was  $< 20 \times 10^9/L$  at baseline, they should at least reach the baseline level.
- Secondary graft failure, defined as  $> 95\%$  recipient cells any time after engraftment with no signs of relapse, or retransplantation because of secondary neutropenia ( $< 0.5 \times 10^9/L$ ) and/or thrombocytopenia ( $< 30 \times 10^9/L$ ).
- Any  $\geq$  Grade 3 nonhematologic toxicities that can be reasonably attributed to study treatment  
Any  $\geq$  Grade 3 nonhematologic toxicities that may be related to underlying GVHD (eg, nausea, vomiting, diarrhea, and rash) will not be considered as DLTs.
- Any  $\geq$  Grade 3 clinical chemistry laboratory abnormalities that are considered clinically significant and that can be reasonably attributed to study treatment. Transient ( $\leq$  72 hours) abnormal laboratory values without associated clinically significant signs and symptoms and not leading to hospitalization will not be considered as DLTs.
- Any toxicity that can be reasonably attributed to study treatment and leading to treatment discontinuation for more than 2 weeks.

Changes in vital signs, clinical evaluations, and clinical laboratory values will be summarized.

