### **5.6.2. Dose-Limiting Toxicity**

A DLT will be defined as the occurrence of any of the toxicities meeting criteria for DLT as defined below, occurring up to and including Day 28, except those with a clear alternative explanation (eg, disease progression) or transient ( $\leq 72$  hours) abnormal laboratory values without associated clinically significant signs or symptoms based on investigator determination. All DLTs will be assessed by the investigator using CTCAE v4.03 criteria.

Individual subject dose reductions may be made based on events observed at any time during treatment with study drug; however, for the purposes of determining the safe and tolerated dose of itacitinib in combination with corticosteroids, decisions will be made based on events that are observed from the first day of study drug administration through and including Day 28. A lower recommended dose may subsequently be determined based on relevant toxicities that become evident after Day 28.

In order to be included in the tolerability review, subjects must have received the cohort-specific dose of itacitinib for at least 75% of the days (ie, 21 days) during the 28-day surveillance period or have experienced a DLT. At each age-specific cohort, additional subjects may be enrolled to achieve a minimum cohort size of approximately 10 subjects, should discontinuation/withdrawal or dose interruptions/reductions result in a subject being nonevaluable. All safety information, including the AE data from the replaced subjects, will be reviewed during the dose tolerability review process.

A DLT is defined as any of the following:

- Grade 4 neutropenia lasting more than 7 days or a  $\geq 90\%$  decrease in ANC from baseline that can reasonably be attributed to study treatment.
- Platelet count  $< 10 \times 10^9/L$  that can be reasonably attributed to study treatment, and does not recover to  $\geq 20 \times 10^9/L$  after 2 weeks. Recovery is defined as platelets  $\geq 20 \times 10^9/L$  in the absence of platelet transfusion in the 7 days preceding the platelet

recovery date. In case the platelet count was  $< 20 \times 10^9/\text{L}$  at baseline, they should at least reach the baseline level.

- Secondary graft failure, defined as  $> 95\%$  recipient cells any time after engraftment with no signs of relapse, or retransplantation because of secondary neutropenia ( $< 0.5 \times 10^9/\text{L}$ ) and/or thrombocytopenia ( $< 30 \times 10^9/\text{L}$ ; [Olsson et al 2013](#)).

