#### **7.6.3. Graft Failure and Donor Chimerism**

Monitoring of graft failure will be primarily based on the monitoring of blood counts with subsequent confirmation by chimerism studies, as clinically indicated. Donor chimerism after a HSCT involves identifying the genetic profiles of the recipient and of the donor and then evaluating the ratio of donor to recipient cells in the recipient's blood, bone marrow, or other tissue. Chimerism testing using peripheral blood or bone marrow will be performed at the treating investigator's discretion according to local institutional practice as indicated in [Table 5](#). In general, genomic polymorphisms should be assessed via polymerase chain reaction analysis of short tandem repeat loci from isolated lymphocytes or myeloid cells. Fluorescence in situ hybridization analysis may also be used in cases with sex-mismatched transplants ([Matsuda et al 2004](#)). If a subject experiences graft failure (ie, initial blood or marrow donor chimerism > 5% declining to < 5% on subsequent measurements), any action taken, including rapid taper of immunosuppression, administration of nonscheduled donor lymphocyte infusion, stem cell boost, or other intervention(s), should be recorded on the appropriate eCRF.

[figure not shown]

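### The retransplantation limb of the secondary graft failure endpoint is narrower than the DLT definition of the same event and can miss late or platelet-only retransplantations

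*Combined protocol and SAP*

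**What the plan says.** The incidence of secondary graft failure is a Phase 2 secondary endpoint, worded the same way in the Synopsis, Table 1 and Section 9.4.2. It has two limbs joined by OR. The first is more than 95% recipient cells at any time after engraftment, without relapse. The second is retransplantation for neutropenia below 0.5 x 10^9/L and/or thrombocytopenia below 20 x 10^9/L. The wording runs "any time after engraftment with no signs of relapse OR retransplantation because of secondary neutropenia" and ends with "within 2 months of transplant".

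Secondary graft failure is also a DLT (Synopsis, Statistical Methods; Section 5.6.2). The two limbs are the same: "recipient cells any time after engraftment with no signs of relapse, or retransplantation because of secondary neutropenia" and/or thrombocytopenia. Here, however, the platelet limit is 30 x 10^9/L and there is no clause tied to the transplant date. DLTs as a class count only up to and including Day 28.

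Section 7.6.3 describes graft failure as "initial blood or marrow donor chimerism > 5% declining to < 5% on subsequent measurements". It leaves chimerism testing to the investigator's discretion and local practice, and it asks for interventions for graft failure to be recorded on the eCRF.

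Section 9.4.2 gives time points for neighbouring endpoints (flares through Day 100, cGVHD at Days 180 and 365) and cumulative incidence for NRM and relapse. For graft failure it gives only an incidence rate, with no start, time point or competing-event rule.

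**The concern.** One named event has two definitions, and the documents do not explain the difference. The endpoint meant to report graft failure is, in its retransplantation limb, the narrower of the two. It can therefore leave out an event that the trial has already counted as graft failure when judging tolerability.

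The clock is a second difficulty. The 2-month clause is anchored to the transplant. Inclusion criteria 3 and 4 require aGVHD and evidence of myeloid engraftment, so part or all of the 2 months has passed by Day 1. Under Section 5.6.4, routine taper of itacitinib starts no earlier than Day 180, unless the medical monitor approves. For subjects treated that long, the limb is closed for most of their exposure.

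Graft failure matters here because Section 1.5 names myelosuppression as a potential effect of the drug. With about 30 subjects per cohort, one uncounted event changes the reported incidence by 1/30 = 3.3 percentage points.

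**Working it through.** The plan gives no expected incidence, precision or coverage figure for graft failure, so there is nothing to reproduce. The check has two parts.

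**1. The definitions side by side**

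| Element | Endpoint (Synopsis, Table 1, 9.4.2) | DLT (Synopsis, 5.6.2) |
|---|---|---|
| Recipient cells | > 95%, any time after engraftment, no relapse | same |
| Neutropenia leading to retransplantation | < 0.5 x 10^9/L | same |
| Thrombocytopenia leading to retransplantation | < 20 x 10^9/L | < 30 x 10^9/L |
| Time clause on retransplantation | 2 months from transplant | none |
| Overall observation limit | not stated | Day 28 |

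Two kinds of event can meet the DLT wording by Day 28 and still fail the endpoint, provided no qualifying chimerism result exists:

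- retransplantation for platelets of 20 to below 30 alone, with neutrophils not below 0.5;
- retransplantation more than 2 months after transplant. With 2 months taken as 60 days, the 28-day DLT period reaches past the window once Day 1 is more than 60 - 28 = 32 days after transplant.

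Section 7.6.3 does not conflict on chimerism: donor cells below 5% is the same condition as recipient cells above 95%.

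**2. Share of treatment days outside the retransplantation limb**

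This part takes the clause to date the retransplantation. Let T be the days from transplant to Day 1 and L the treatment length in days. Neither T nor the actual L is in the documents, so both are assumed over a range.

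Share outside = 1 - max(0, min(60 - T, L)) / L

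| T (days) | L = 28 | L = 100 | L = 180 |
|---|---|---|---|
| 0 | 0% | 40% | 67% |
| 14 | 0% | 54% | 74% |
| 28 | 0% | 68% | 82% |
| 42 | 36% | 82% | 90% |
| 60 or more | 100% | 100% | 100% |

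Worked cases for L = 180:

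- T = 0: 1 - 60/180 = 67%. This is a floor, because T cannot be zero when engraftment and aGVHD come before entry.
- T = 28: 1 - 32/180 = 82%.
- T = 60: 1 - 0/180 = 100%.

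Taking 2 months as 61 days moves the floor only to 1 - 61/180 = 66%.

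More than half of treatment is outside the limb when L > 2 x (60 - T). That is beyond 120 days at T = 0, 92 at T = 14, 64 at T = 28 and 36 at T = 42.

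For the chimerism limb the share outside is 0% at every T and L, because it has no time limit.

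**The case against.** A reader might infer that the endpoint as a whole excludes most of the on-treatment period. The documents do not support that. The chimerism limb runs at any time after engraftment, and Section 7.6.3 has blood-count monitoring followed by chimerism confirmation as clinically indicated. A late failure confirmed in that way is counted. What remains is the late retransplantation without a qualifying result, which is possible because testing is discretionary.

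A reader might also infer that the DLT definition is open-ended. It is not. It lacks the 2-month clause but stops at Day 28, and so covers less of treatment than the chimerism limb does.

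The size is also open to challenge:

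- Day 180 is the earliest routine taper for subjects in CR or VGPR, not a stated treatment duration.
- Section 5.7.1 requires withdrawal for progression or lack of response, and in the adult study 15 of 29 participants stopped because of a TEAE (Section 1.4.2). For a subject who stops at Day 28 and started within 28 days of transplant, nothing is excluded.
- A share of days is not a share of events.
- The 20-against-30 gap affects only retransplantations triggered by platelets alone, since the neutropenia limit is identical.

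The 2-month clause could instead date the cytopenia. A late retransplantation for an early cytopenia would then count. The text does not settle this, and two analysts could count differently.

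Finally, these events are not lost to safety reporting. A retransplantation would ordinarily meet the SAE criteria in Section 8.3.1, and interventions for graft failure go on the eCRF. This stands, but it does not correct the incidence that the endpoint reports.

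These points limit the concern to one limb and make its size conditional. They do not explain why the two definitions differ.

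**Conclusion.** The point holds for the retransplantation limb only. The endpoint and the DLT differ on the platelet threshold (20 against 30 x 10^9/L) and on the transplant-anchored clause, without explanation. Without a qualifying chimerism result, the endpoint misses a retransplantation for cytopenia more than 2 months after transplant, or one for platelets of 20 to below 30 alone, although either can count as a DLT if it occurs by Day 28.

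If the clause dates the retransplantation, at least 67% of treatment days lie outside this limb for a subject treated to Day 180. The share is 82% if Day 1 is 28 days after transplant and 100% at 60 days or more. For short treatment it can be 0%. These figures assume 2 months = 60 days and an assumed time from transplant to Day 1. They describe exposure time, not the number of events missed, which the documents give no basis to estimate.

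A reader might conclude that one platelet threshold must apply everywhere. The documents do not establish that: the DLT criterion feeds the study-termination rule in Sections 4.1 and 9.8, and a different definition there may be deliberate. This review does not say which threshold is right.

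**What to change.** In the Synopsis, Table 1 and Section 9.4.2:

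- Remove the 2-month-from-transplant limit from the endpoint.
- Count secondary graft failure from Day 1 over the period in which the trial already collects graft failure data, and state that period.
- Report cumulative incidence with death and relapse as competing events, in line with the treatment of NRM and relapse in Section 9.4.2.

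Reconcile the platelet threshold between the endpoint text and the DLT text (Synopsis and Section 5.6.2), or state why they differ.

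The cost is minor rewording, and the reported incidence may be slightly higher. Section 7.6.3 already puts interventions for graft failure on the eCRF. The counting period should not go beyond existing collection without a check: survival follow-up in Section 6.5.3 covers only new GVHD therapy and survival status, and chimerism testing is discretionary. Counting to the end of all follow-up could therefore need additional data.
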